4.7 Safety Analysis

All safety summary tables (as applicable) and listings will be presented.

Safety will be assessed by the incidence of AEs and TEAEs, study discontinuation information, physical examinations, clinical laboratory evaluations, ECGs, and vital signs measurements.

Safety variables will be tabulated (where applicable) and presented for all participants in the safety population. Adverse events will be summarized by MedDRA system organ class, preferred term, and treatment. All safety assessments will be listed.

4.7.1 Study Product Exposure

Exposure to study drug will be listed by participant, treatment sequence, and treatment received, indicating dose date and time. Any deviations will be documented as specified under the Protocol Deviations section and listed separate from the study exposure.

4.7.2 Adverse Events

All AEs occurring during the study, from the signing of informed consent to approximately 7 days following the last study drug administration, including the washout intervals, will be documented on the eCRF. All AEs will be coded and classified according to MedDRA (version 25.1 or higher). Their severity will be graded by the investigator using the National Cancer Institute Common Terminology Criteria for Adverse Events (NCI CTCAE) 5.0 or the current version. Adverse events which occur prior to the date and time of the first dose of study drug are considered non-treatment emergent events. Adverse events which occur on or after the date and time of the first dose of study drug up to approximately 7 days following the last drug administration are considered treatment emergent adverse events. Adverse events occurring during a treatment period will be summarized under the treatment received when the AE started. Adverse Events that occur during a washout period will be attributed to the prior treatment.

All treatment emergent AEs (TEAEs) and AEs of special interest (AESIs) will be summarized as the number and percentage of participants by System Organ Class, Preferred Term, and treatment sequence (and overall). Separate summaries will be created by severity and by relationship to study drug. If the same AE (preferred term) is reported more than once for the same participant, it will only be counted once in the summary table. For summary tables by severity and relationship to study drug, if the same AE (preferred term) is reported more than once for the same participant, the highest severity grade (severe > moderate > mild) or the strongest relationship to treatment (related > not related) will be counted in the summary table.

All AEs will be listed, and those that are treatment-emergent will be identified.

All Serious Adverse Events (SAEs) including any deaths will be listed by participants.

All AEs leading to study discontinuation will be listed by participants.

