### **7.8. Safety Analysis**

Safety will be assessed by evaluation of AEs, physical examinations, clinical laboratory evaluations, ECGs, and vital signs measurements. AEs will be coded by system organ class and preferred term using the Medical Dictionary for Regulatory Activities (MedDRA) (version 25.1

[released September 2022] or the current version). The occurrence of TEAEs and AESIs will be presented by system organ class and preferred term by treatment. Additionally, TEAEs and AESIs will be presented by treatment for each relationship and severity with the most closely related or most severe presented for events that occurred more than once. A listing of SAEs will be provided, if applicable.

Physical examination findings will be provided in a data listing.

The overall interpretation of the ECG result will be presented as normal, abnormal (not clinically significant) and abnormal (clinically significant) for each day, by treatment. Descriptive statistics will be presented for the ECG measurements and change from baseline collected at each day by treatment.

For the continuous laboratory parameters, descriptive statistics will be presented for each day and for the changes from baseline to each day by treatment. Additionally, parameters will be categorized as low, normal, or high according to laboratory range specifications and the number and percentage of participants will be presented by treatment.

For each vital sign measurement and changes from baseline at each time point, descriptive statistics will be presented by treatment.

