2.3 Endpoints

Primary:

- Relative bioavailability comparison of 300 mg neat ARN-75039 in HPMC capsules (Treatment A; reference) to 300 mg ARN-75039 with excipients tablets (Treatment B; comparator) following oral administration under fed conditions.
- PK parameters of 300 mg ARN-75039 with excipients tablets and 300 mg neat ARN-75039 in HPMC capsules, including but not limited to:
 - Area under the plasma concentration-time curve from time zero to time of last quantifiable concentration (AUC_{0-t}).
 - Area under the plasma concentration-time curve from time zero to 24 hours post-dose (AUC_{0-24}).
 - Area under plasma concentration-time curve from time zero to infinity ($AUC_{0-\infty}$).
 - Maximum observed plasma concentration (C_{max}).

- Minimum observed plasma concentration from time zero to 24 hours post-dose $C_{min0-24}$.
- Time to reach C_{max} (t_{max}).
- Half-life ($t_{1/2}$).
- Apparent clearance after extravascular administration (CL/F).
- Apparent volume of distribution during the terminal phase after extravascular administration (V_z/F).

Secondary:

- Type and frequency of treatment-emergent adverse events (TEAEs).
- Type and frequency of treatment-emergent serious adverse events (TESAEs).
- Type and frequency of study drug-related >Grade 1 TEAEs.
- Type and frequency of changes in clinical laboratory values, ECGs, colonic transit time (biomarker), physical examinations, and vital signs.

3 Study Design and Methods

ARN-75039-103 is a comparative, randomized, single-dose, crossover study to assess the PK, safety, and tolerability of neat ARN-75039 in hydroxypropyl methylcellulose (HPMC) capsules against ARN-75039 with excipients in tablet form administered by the oral route in healthy adult participants. The safety assessments will include assessments of vital signs, clinical laboratory values, and ECGs.

A total of 16 participants were randomized 1:1 into one of the following two sequences:

Sequence 1:

[figure not shown]
- Period 1: 300 mg neat ARN-75039 in HPMC capsules (Treatment A; reference product)
- Period 2: 300 mg ARN-75039 with excipients in tablet form (Treatment B; comparator)

Sequence 2:

- Period 1: 300 mg ARN-75039 with excipients in tablet form (Treatment B; comparator)
- Period 2: 300 mg neat ARN-75039 in HPMC capsules (Treatment A; reference product)

A study scheme is provided below:

Sequence 1

Sequence 2

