3.3 Sample Size Justification

The sample size of 16 evaluable participants proposed for this study was not based on statistical analysis assessments but was judged to provide a sufficient dataset to be able to make direct comparisons in pharmacokinetic parameter estimates between the reference

and test groups in this clinical study. Participants withdrawn due to a study drug-related Grade >1 TEAE will not be replaced. Participants who are withdrawn due to a study drug-related Grade 1 TEAE may be replaced. Participants who are withdrawn due to a reason other than a drug-related TEAE during the Treatment Period may be replaced as necessary to obtain 16 evaluable participants at the end of the clinical study.

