4.7.3 Clinical Laboratory Assessments

Clinical laboratory test parameters (refer to [Table 2](#)), with associated reference ranges provided by the laboratory, will be listed for individual participants by treatment sequence and time point. Clinical laboratory test results outside the laboratory's reference ranges will be flagged with "L" for low and "H" for high.

The summary may be produced for blood chemistry and hematology numeric tests only, and would include descriptive statistics for baseline, all post-baseline, and change from baseline values by treatment sequence.

Table 2: Clinical Laboratory Tests

Hematology:		Serum Chemistry:	
• Hematocrit	• RBC count	• Glucose	• Direct bilirubin
• Hemoglobin	• WBC count – with differential	• BUN	• Total bilirubin
• Platelet count		• Creatinine	• Sodium
Coagulation:		• Total bilirubin	• Potassium
• PT/INR	• PTT	• AST	• Total CO ₂
Urinalysis:		• ALT	• Chloride
• Bilirubin	• Glucose	• GGT	• Calcium
• pH	• Nitrates	• Alkaline phosphatase	• Inorganic phosphate
• Specific gravity	• Ketones	• Creatine kinase	• Magnesium
• Protein	• Blood	• Total protein	• eGFR
• Leukocytes	• Microscopic urine analysis		
• Urobilinogen			

Urine Drug Screen: 
 • Amphetamines • Barbiturates • Opiates • Benzodianses • Cocaine metabolites • Cannabinoids 	
 • Lactate dehydrogenase
Pregnancy Testing: 
 • Serum hCG – at Screening • Urine hCG – at the time of study center admission and Day 15 Discharge or ET 	Post-Menopausal Status Testing: 
 • FSH • Estradiol
Alcohol Screening: 
 • Breath alcohol test 	

Abbreviations: ALT = alanine aminotransferase; AST = aspartate aminotransferase; BUN = blood urea nitrogen; CO₂ = carbon dioxide; eGFR = estimated glomerular filtration rate; FSH = follicle-stimulating hormone; GGT = gamma-glutamyl transferase; hCG = human chorionic gonadotropin; INR = international normalized ratio; PT = prothrombin time; PTT = partial thromboplastin time; RBC = red blood cell; WBC = white blood cell.

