4.7.4 Vital Signs Assessments

Vital signs, including systolic (SBP) and diastolic blood pressure (DBP), heart rate, respiration rate, and oral temperature are measured at the time points indicated in the SOA (Table 1). Vital signs (except for height and weight and BMI collected at Screening only) will be monitored periodically during and following study of drug administration. The investigator may repeat the vital signs if deemed appropriate.

All assessments will be listed by participant, treatment sequence, and visit.

A summary table will be produced and will include descriptive statistics for baseline, post-baseline, and change from baseline values by treatment sequence for each vital sign parameter (this will not include BMI which is calculated at screening).

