4.7.6 Electrocardiogram

Electrocardiograms (ECGs) will be performed at screening, admission, pre-dose, on dosing days Day 1 in each period (3–6h post-dose, approximate C_{max}), and on Day 15 or at the early termination (ET) visit with all measurements taken within 5 minutes apart. ECG time points are indicated in the SOA (Table 1). The date and time of each ECG and its results will be documented in the source documents and transcribed into the eCRF.

Electrocardiograms may be performed at any time during the study in the interest of subject's safety at the discretion of the Investigator.

The overall interpretation of the ECG result will be presented as normal, abnormal (not clinically significant) and abnormal (clinically significant) for each day, by treatment. Descriptive statistics will be presented for the ECG measurements and change from baseline collected each day by treatment sequence.

The ECG parameters will be listed by participant, treatment sequence, and visit.

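### SAP safety summaries are grouped by treatment sequence where the protocol requires grouping by treatment, so the adverse event tables as specified would not show a formulation difference

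*SAP*

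**What the plan says.** Protocol 7.8 groups every safety summary by treatment. For adverse events it says "The occurrence of TEAEs and AESIs will be presented by system organ class and preferred term by treatment", and it repeats that grouping for relationship and severity, ECG measurements, laboratory parameters and vital signs. Laboratory summaries are to be shown for each day, and vital signs at each time point.

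The SAP agrees in its general safety section (4.7): "Adverse events will be summarized by MedDRA system organ class, preferred term, and treatment". Section 4.7.2 also assigns each event to the treatment received at onset, and events in the washout to the preceding treatment.

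The table specifications then use a different grouping:

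- 4.7.2: TEAEs and AESIs are "summarized as the number and percentage of participants by System Organ Class, Preferred Term, and treatment sequence (and overall", with separate summaries by severity and by relationship.
- 4.7.3: the laboratory summary, which is worded as optional, gives "descriptive statistics for baseline, all post-baseline, and change from baseline values by treatment sequence".
- 4.7.4: the vital signs table gives "change from baseline values by treatment sequence for each vital sign parameter".
- 4.7.6: "Descriptive statistics will be presented for the ECG measurements and change from baseline collected each day by treatment sequence". The overall ECG interpretation in the same section stays by treatment, as in the protocol.

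The SAP gives no reason for the change.

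**The concern.** In a two-period crossover, sequence is the order of dosing, not a treatment. Sequence 1 takes capsule then tablet, and Sequence 2 takes tablet then capsule. A sequence column that pools both periods therefore mixes the two products, and comparing the two columns does not compare the formulations.

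The comparison is one the protocol asked for, and it is a reasonable question here. Protocol 6.12.6 names elevated heart rate among the events to monitor. The telemetered dogs in Protocol 1.2.6 showed heart-rate increases of up to 38% and corrected QT increases of up to 9%. In Protocol Table 2 the mean dog Cmax was 5346 ng/mL for the prototype 5 tablet and 4518 ng/mL for the capsule, a ratio of 5346/4518 = 1.18. If the tablet peaks higher in people too, the by-treatment safety tables are where a related tolerability difference would show.

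A second gap sits in the same section. Drug-related TEAEs above Grade 1 are a listed secondary endpoint (SAP 2.3), but 4.7.2 specifies only separate severity and relationship tables.

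**Working it through.** The plan has no figure of its own to reproduce. No safety comparison is powered, and the SAP says that the sample size "was not based on statistical analysis assessments". The check is a comparison of texts followed by expected counts.

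**Texts side by side**

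| Summary | Protocol 7.8 | SAP |
|---|---|---|
| TEAEs and AESIs, including by severity and relationship | treatment | 4.7: treatment; 4.7.2: sequence and overall |
| Laboratory values | treatment, each day | 4.7.3: sequence; time point mentioned for listings only |
| Vital signs | treatment, each time point | 4.7.4: sequence; visit mentioned for listings only |
| ECG measurements and change | treatment, each day | 4.7.6: sequence, each day |
| ECG overall interpretation | treatment | 4.7.6: treatment |

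**Inputs for the counts.** SAP Section 3 states: "A total of 16 participants were randomized 1:1 into one of the following two sequences". That gives 16/2 = 8 per sequence if balanced. Event rates are assumptions: pA on capsule and pB on tablet. I also assume that all 16 receive both doses and that there are no period or carryover effects.

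**Formulas.**

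- By sequence, pooled over periods with independent events: P(at least one event) = 1 − (1 − pA)(1 − pB). Swapping the order of A and B leaves this unchanged, so both columns have the same expectation.
- By treatment: expected counts of 16 × pA and 16 × pB.

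| pA (capsule) | pB (tablet) | Each sequence column | By treatment, A vs B |
|---|---|---|---|
| 10% | 10% | 1 − 0.9 × 0.9 = 19%, 1.52 of 8 | 1.6 vs 1.6 of 16 |
| 10% | 30% | 1 − 0.9 × 0.7 = 37%, 2.96 of 8 | 1.6 vs 4.8 of 16 |
| 10% | 40% | 1 − 0.9 × 0.6 = 46%, 3.68 of 8 | 1.6 vs 6.4 of 16 |
| 10% | 50% | 1 − 0.9 × 0.5 = 55%, 4.4 of 8 | 1.6 vs 8 of 16 |
| 5% | 25% | 1 − 0.95 × 0.75 = 28.75%, 2.3 of 8 | 0.8 vs 4 of 16 |

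The expected difference between sequence columns is zero in every row. Independence affects only the level. With 10% and 40%, the pooled rate lies between 40% (everyone with an event on capsule also has one on tablet) and 10% + 40% = 50% (no overlap). Whatever the value, it is the same in both columns.

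**Continuous measures.** If post-baseline changes were pooled over both periods with equal numbers of readings, an assumed mean change of 0 on capsule and 10 on tablet would give (0 + 10)/2 = 5 in each sequence column. If results are shown by day or visit, formulation can be recovered: Sequence 1 Day 1 is capsule, Sequence 1 Day 8 is tablet, and Sequence 2 is the reverse. A reader must then combine opposite periods from two columns of about 8, where a by-treatment table would give 16 per formulation. ECG is specified by day. The summary text for laboratory values and vital signs does not say.

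**Related TEAEs above Grade 1.** Take one participant with an unrelated Grade 2 event and a related Grade 1 event of the same preferred term. Section 4.7.2 counts this participant at Grade 2 in the severity table and as related in the relationship table. A participant with one related Grade 2 event produces the same two entries. Only the second meets the endpoint, so the two tables together cannot give its count.

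**The case against.** The strongest reply is that this is a wording conflict in descriptive secondary tables for 16 people, and that no data are lost. Much of that stands. All adverse events and safety assessments are listed, dosing is listed by treatment received with date and time (SAP 4.7.1), and baseline is defined per period (SAP 3.4). For adverse events the SAP is inconsistent with itself and has not plainly chosen sequence. The table shells, which fix the final layout, are not among the documents, so they may already be by treatment.

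Three stronger readings are tempting, and the documents do not support them:

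- *The secondary safety objective goes unanswered.* SAP 2.2 asks for further safety and tolerability information on ARN-75039 and states no formulation contrast. The overall column for adverse events serves that objective. The by-treatment requirement comes from Protocol 7.8 and from the design statement, which sets capsules against tablets.
- *A formulation difference in safety cannot be seen at all.* Listings allow it to be rebuilt, the ECG interpretation is already by treatment, and ECG statistics by day within sequence still identify the formulation.
- *ECG effects are averaged away within a day.* The per-day wording is also the protocol's, and neither document says that time points within a day are averaged.

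The reply does not remove the conflict. Followed literally, 4.7.2 gives adverse event tables that cannot display the result Protocol 7.8 requires, and its attribution rule would have no role in those tables.

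**Conclusion.** The point holds for the specified summary tables. SAP 4.7.2, 4.7.3, 4.7.4 and the ECG measurements in 4.7.6 depart from Protocol 7.8 without explanation. For adverse events, 4.7.2 also conflicts with SAP 4.7 and with its own attribution rule.

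The effect is greatest for adverse events. Pooled over periods, an assumed 30-point difference (40% against 10%) has an expected difference of zero between the columns. This rests on no period or carryover effects. If such effects exist, the columns may differ, but the difference would still not estimate the formulation contrast. For ECG by day, and for laboratory values and vital signs if laid out by visit, the cost is a comparison split into cells of about 8. Separately, no table specified in the SAP text reports drug-related TEAEs above Grade 1.

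This should be corrected before the tables are run. It affects how safety results are displayed, not data collection or the pharmacokinetic analysis.

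**What to change.** 1. In SAP 4.7.2 (including the severity and relationship tables), 4.7.3, 4.7.4 and the ECG measurements in 4.7.6, change the summary columns to treatment received (A capsule, B tablet) plus overall. Use the participants dosed with each formulation as denominators, and apply the existing attribution rule. Keep sequence for listings.
2. Restore the protocol's layout in the summaries: each day for laboratory values and each time point for vital signs.
3. Add one table of participants with a study drug-related TEAE above Grade 1, by treatment, counting an event only if it meets both conditions.
4. Optionally, state the nominal time points at which ECG measurements will be summarised. This is a clarification, not the correction of a departure from the protocol.

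The cost is SAP wording and table shells, with no new data. SAP Section 1 allows only minor changes to tables once the SAP is final, so this should be settled first. If the SAP is already final, Section 4.10 provides for documenting the change.

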4.7.3 Clinical Laboratory Assessments

Clinical laboratory test parameters (refer to [Table 2](#)), with associated reference ranges provided by the laboratory, will be listed for individual participants by treatment sequence and time point. Clinical laboratory test results outside the laboratory's reference ranges will be flagged with "L" for low and "H" for high.

The summary may be produced for blood chemistry and hematology numeric tests only, and would include descriptive statistics for baseline, all post-baseline, and change from baseline values by treatment sequence.

Table 2: Clinical Laboratory Tests

Hematology:		Serum Chemistry:	
• Hematocrit	• RBC count	• Glucose	• Direct bilirubin
• Hemoglobin	• WBC count – with differential	• BUN	• Total bilirubin
• Platelet count		• Creatinine	• Sodium
Coagulation:		• Total bilirubin	• Potassium
• PT/INR	• PTT	• AST	• Total CO ₂
Urinalysis:		• ALT	• Chloride
• Bilirubin	• Glucose	• GGT	• Calcium
• pH	• Nitrates	• Alkaline phosphatase	• Inorganic phosphate
• Specific gravity	• Ketones	• Creatine kinase	• Magnesium
• Protein	• Blood	• Total protein	• eGFR
• Leukocytes	• Microscopic urine analysis		
• Urobilinogen			

Urine Drug Screen: 
 • Amphetamines • Barbiturates • Opiates • Benzodianses • Cocaine metabolites • Cannabinoids 	
 • Lactate dehydrogenase
Pregnancy Testing: 
 • Serum hCG – at Screening • Urine hCG – at the time of study center admission and Day 15 Discharge or ET 	Post-Menopausal Status Testing: 
 • FSH • Estradiol
Alcohol Screening: 
 • Breath alcohol test 	

Abbreviations: ALT = alanine aminotransferase; AST = aspartate aminotransferase; BUN = blood urea nitrogen; CO₂ = carbon dioxide; eGFR = estimated glomerular filtration rate; FSH = follicle-stimulating hormone; GGT = gamma-glutamyl transferase; hCG = human chorionic gonadotropin; INR = international normalized ratio; PT = prothrombin time; PTT = partial thromboplastin time; RBC = red blood cell; WBC = white blood cell.

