### Statistical Methods:

The sample size has been selected in accordance with standard designs for Phase 1 assessments of PK, safety, and tolerability. The primary analysis will describe the PK characteristics of the two drug products. PK samples will be collected at pre-specified time points.

The PK parameters to be assessed include but are not limited to:

- Cmax maximum plasma concentration
- Cmin0-24 minimum plasma concentration from time zero to 24 hours post-dose
- tmax time of maximum plasma concentration
- λz terminal-phase rate constant
- t½ elimination half-life
- AUC0-24 area under the plasma concentration-time curve from time zero to 24 hours post-

	dosing
• $AUC_{0-t}$	area under the plasma concentration-time curve from time zero to time t (time of last quantifiable plasma concentration)
• $AUC_{0-\infty}$	area under the plasma concentration-time curve from time zero to infinity
• $CL/F$	apparent clearance
• $MRT$	mean residence time
• $V_z/F$	apparent volume of distribution

The secondary endpoints will describe the incidence of adverse events and laboratory abnormalities. Adverse events will be coded according to system organ class and preferred term using the Medical Dictionary for Regulatory Activities (MedDRA) (version 25.1 [released September 2022] or the current version). Their severity will be graded using the National Cancer Institute Common Terminology Criteria for Adverse Events (NCI CTCAE) 5.0 or the current version. Adverse events will be organized by system organ class and preferred term. The vital signs, ECG findings, and physical examination data and change of hematologic and chemistry parameters from baseline will be summarized for each post-baseline visit. Hematologic and chemistry parameters will be categorized as low, normal, or high based on laboratory normal ranges and presented as shifts from baseline. A detailed description of data analyses and statistical methods will be outlined separately in the Statistical Analysis Plan.
	
Date: 29 January 2025	

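### SAP 4.7.3 makes the laboratory summary optional, narrows it and groups it by sequence, although Protocol 7.8 promises laboratory statistics and low/normal/high counts by treatment

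*SAP*

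**What the plan says.** **Protocol.** Section 7.8 says that for continuous laboratory parameters "descriptive statistics will be presented for each day and for the changes from baseline to each day by treatment". It then calls for results "categorized as low, normal, or high according to laboratory range specifications and the number and percentage of participants will be presented by treatment". The synopsis, under Statistical Methods, says that hematologic and chemistry parameters will be "categorized as low, normal, or high based on laboratory normal ranges and presented as shifts from baseline".

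**SAP.** Section 4.7.3 says that the laboratory parameters "will be listed for individual participants by treatment sequence and time point", with out-of-range results flagged L or H. On tabulation it says: "The summary may be produced for blood chemistry and hematology numeric tests only". If made, that summary would hold "descriptive statistics for baseline, all post-baseline, and change from baseline values by treatment sequence". Section 2.3 still lists as a secondary endpoint: "Type and frequency of changes in clinical laboratory values, ECGs, colonic transit time (biomarker), physical examinations, and vital signs".

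**The concern.** The two documents describe different laboratory outputs, and the SAP gives no reason for the change. A listing gives no frequency of anything, and an optional table of means by sequence gives no frequency of change. The laboratory component of the secondary endpoint could therefore reach the report with no table that counts participants, and with none organised by formulation.

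Two features of the study make this worth correcting. Protocol 1.2.3 names bone marrow among the target organs in both rats and dogs, so a reader will look at hematology. Protocol 5.2 says that the study is open label, so a table left optional can be kept or dropped after results have been seen.

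**Working it through.** The plan states no figure on this point, so the check is a comparison of texts, with simple arithmetic on the layout.

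**1. The commitments side by side**

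| Element | Protocol | SAP 4.7.3 |
|---|---|---|
| Status of the summary | Firm (7.8) | Optional |
| Tests covered | Continuous laboratory parameters in general (7.8); hematology and chemistry (synopsis) | Numeric chemistry and hematology only |
| Grouping | Treatment (7.8) | Treatment sequence |
| Low/normal/high counts | Yes, by treatment (7.8) | None; L and H flags in the listing |
| Shifts from baseline | Yes, hematology and chemistry (synopsis) | None |

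Status, grouping, counts and shifts all differ. Scope differs from 7.8 but matches the synopsis.

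**2. Whether other SAP text restores the tables**

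SAP 4.7 says in general that safety variables are tabulated, but only where that applies. SAP 4.2 sends the reader to the individual sections for the safety tables, so 4.7.3 governs. The weak wording is particular to laboratory data: for vital signs, SAP 4.7.4 commits firmly to a summary table.

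**3. What a by-sequence table would show**

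SAP section 3 gives 16 participants randomised 1:1, so 16 / 2 = 8 per sequence. At the 24-hour draws the layout is:

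| Column | Day 2 | Day 9 |
|---|---|---|
| Sequence 1 (n = 8) | capsule | tablet |
| Sequence 2 (n = 8) | tablet | capsule |

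Each column holds both formulations, and each formulation is split over two columns and two days. A table by treatment at 24 hours would pool 8 + 8 = 16 per formulation if everyone completes both periods.

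**4. Whether a by-treatment table can be built**

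SAP 3.4 defines a baseline for each period. Both schedules of assessments place hematology, chemistry and coagulation at Day -1, Day 2, Day 7, Day 9 and Day 15 (or early termination), with doses on Days 1 and 8. Times after dosing are:

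- Day 2: (2 − 1) × 24 = 24 hours. Day 9: (9 − 8) × 24 = 24 hours. These match.
- Day 7: (7 − 1) × 24 = 144 hours. Day 15: (15 − 8) × 24 = 168 hours. These do not match, so the end-of-period row needs a label giving both times.

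Day 7 is also the last scheduled draw before the second dose, so it serves both as the end of Period 1 and as the Period 2 baseline. The 24-hour table can be built directly. The end-of-period table can be built once its time point is defined.

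**The case against.** The case against runs as follows, with what stands of each part.

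- **Detail belongs in the SAP, and the shells may hold the tables.** The protocol defers detail to the SAP, and SAP sections 1 and 4.9 refer to table shells that were not supplied. A reader might infer that no shift or category table will be produced. The documents support only that the SAP text specifies none. Deferring detail, however, does not cover making a promised analysis optional or leaving it out.
- **The endpoint does not ask for a comparison.** This stands. The secondary objective is additional safety and tolerability information, not tablet against capsule. The by-formulation requirement comes from Protocol 7.8 alone.
- **Shifts by treatment.** A reader might infer that Protocol 7.8 requires shift tables by treatment. It does not: 7.8 asks for category counts by treatment. Shifts appear only in the synopsis, which does not say how they are grouped.
- **Coagulation.** A reader might infer that the SAP simply forgot it. The synopsis is as narrow as the SAP, and only the general wording of 7.8 reaches PT/INR and PTT. This is an inconsistency inside the protocol that the SAP has to settle. Coagulation is still listed and flagged.
- **Precision.** A reader might infer a material loss of precision from cells of 8 instead of 16: with equal standard deviations, √(16/8) = 1.41 on a standard error. No laboratory inference or precision target is planned, so no decision turns on that ratio. Sequence and day together identify the formulation. With 8 and 8, the pooled mean is the average of two printed cells, provided the optional table is made.
- **Reticulocytes.** A reader might infer that shift tables are needed to follow the reduced reticulocytes seen in dogs. Reticulocytes are in neither document's laboratory panel. The dog hematology findings were at the high-dose level after 14 days of repeat dosing, whereas this trial gives two single doses.
- **Grouping is not special to laboratory data.** The SAP also groups adverse events, vital signs and ECG measurements by sequence. That element should not add weight here, though any correction should be consistent across them.

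**Conclusion.** The conflict is real, and the SAP text is wrong as written, not merely short of detail. It replaces a firm by-treatment commitment with an optional by-sequence one, and it specifies none of the low/normal/high counts or shifts that the protocol promises.

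Its size is modest. It affects the laboratory component of one descriptive secondary endpoint in 16 participants and leaves the primary pharmacokinetic analysis alone. With 16 participants, counts could be made by hand from the flagged listing, but that does not replace the table Protocol 7.8 promises.

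The conclusion rests on the SAP text governing the output. If the shells already contain the protocol's tables, the remaining step is to bring the SAP wording into line with them.

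**What to change.** In SAP 4.7.3:

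1. Make the summary firm by changing *may* to *will*.
2. Summarise values and change from the period baseline by treatment at defined post-dose times: 24 hours (Days 2 and 9), and end of period (Day 7 for Period 1, Day 15 for Period 2), labelled as about 144 and 168 hours.
3. Add low/normal/high counts and percentages by treatment, as in Protocol 7.8.
4. Add shifts from baseline for hematology and chemistry, as in the synopsis.
5. For coagulation, reconcile the wider scope of Protocol 7.8 with the narrower scope of the synopsis. Then either include the numeric tests or state why they are only listed.

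The cost is a few extra descriptive tables from samples already scheduled, using a baseline that SAP 3.4 already defines. SAP section 1 allows only minor table changes once the SAP is final, so the commitment belongs in the SAP text itself.
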